4.2 Informed Consent

Informed consent will be obtained under the conditions set forth in 21 CFR Part 50: a) the subject shall have sufficient opportunity to consider participation in the study, b) informed consent shall be obtained without coercion or undue influence, c) informed consent shall be written in the native language of the subject and administered by approved personnel who speak the native language of the subject, d) a subject cannot be led to believe that they are waiving their rights as a subject or the liability of the sponsor or investigator.

Informed Consent Forms will be signed and dated by the subject prior to the completion of any study-specific procedures. Consent will be administered by the investigator or other person authorized by the Institutional Review Board (IRB) such as a study coordinator or a translator. A copy of the Informed Consent Form once signed and dated will be provided to the subject.

Subjects will be considered enrolled in the study after consent has been obtained.

Informed Consent Forms will follow the format of elements presented in 21 CFR Part 50.25. See **Appendix C – Informed Consent Form.**

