4.4.2 Laboratory Tests

Blood samples will be drawn for complete blood count (CBC), prothrombin time (PT), and partial thromboplastin time (PTT).

Urine samples will be obtained if there is any question of an active urinary tract infection.

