4.6.12 Physical Examination

All subjects will undergo a standard physical examination during the Baseline visit and at the 1, 3, 6, 9, and 12 month follow-up visits. The baseline physical exam should be completed within 30 days prior to treatment with the NanoKnife System.

On the day of treatment, the subject will be evaluated for any changes to physical exam as compared to the baseline assessment during an abbreviated physical exam prior to treatment with the NanoKnife System.

4.6.13 *Laboratory Tests*

Blood samples will also be collected at the Baseline visit and the 1, 3, 6, 9, and 12 month follow-up visits via standard forearm venipuncture, for assessment of serum PSA. Complete Blood Count will also be assessed at Baseline.

Urine samples will be collected pre-treatment, and at any subsequent follow-up visits if there is a question of an active urinary tract infection.

4.6.15 *Radiologic Procedures*

As the biopsy needles and NanoKnife electrode probes will be surgically placed into the prostate tissue under TRUS or MRI/TRUS fusion guidance, images of the prostate will be taken using this radiologic method to confirm the prostate is satisfactorily visible in sagittal and axial views.

Transrectal ultrasound will be conducted by the investigator according to standard accepted TRUS procedures. Subjects will be instructed to discontinue blood-thinning medications (e.g., aspirin, ibuprofen) for a week to 10 days prior to undergoing TRUS. Before undergoing the procedure, subjects will be instructed to drink a few glasses of water because a full bladder can improve visualization of the prostate gland. An enema may be administered to cleanse the bowel prior to the procedure.

Standardized measurements of the anterior/posterior, width and length of the prostate will be made. The measurements will be recorded on the ultrasound images maintained in the CRF. The ultrasound images will be saved in the study file.

The transrectal ultrasound procedure will also be used during the transperineal or transrectal prostate biopsy (at screening, at the 12-month follow-up visit, and if indicated by rising PSA) and during the NanoKnife System procedure.

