mpMRI imaging of the prostate using utilizing the Prostate Imaging – Reporting and Data System Version 2.1 (PI-RADS version 2.1) will be conducted to document the location of the lesion and to characterize post-treatment effects and their correlation with outcome. The protocol including the recommended standardized protocol is presented in **Appendix A – Standard Operating Procedure: 1. mpMRI Protocol.**

4.6.16 *Disease Assessment Procedures*

The grade and location of the subject's prostate lesion will be assessed by the following procedures:

Determination of Prostate Specific Antigen (PSA):

Blood samples, as obtained from the above laboratory test procedure, will be used to determine the subject's serum PSA during the screening visit.

Serum PSA will also be assessed at the 1, 3, 6, 9, and 12 month follow-up visits to assess the effectiveness of therapy by measurement of prostate-specific antigen (PSA) kinetics including PSA nadir, time to PSA nadir and post-nadir PSA stability through 12 months post-treatment.

Study subjects who are found to be biochemical failures as defined by the Phoenix definition of nadir + 2 ng/mL, and subjects who have clinical suspicion, will be re-biopsied as explained below.

Transperineal or Transrectal Prostate Biopsy:

Pre-Treatment Biopsy and 12-Month Post-Operative Biopsy: The location and grade of the subject's prostate lesion will be documented via transrectal ultrasound-guided prostate biopsy (template mapping and/or targeted biopsy of lesion plus 10-14 core systematic sampling to include adequate sampling of the peripheral zone) for the screening biopsy and the biopsy performed at 12 months post-NanoKnife System procedure. The biopsy can be performed with either transperineal or transrectal biopsies to MR-visible lesions and 10-14 core systematic sampling to the peripheral zone. Three-dimensional data on the location and specific grade for each lesion is used for NanoKnife System ablation planning.¹¹

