	Screening	Baseline ³	NanoKnife Treatment		1 month 30 ± 7 days	3 months 90 ± 14 days	6 months 180 ± 14 days	9 months 270 ± 14 days	12 months 365 ± 28 days
Informed Consent ¹	X								
Enrollment	X								
Medical History	X								
Standard Physical Exam		X			X	X	X	X	X
Abbreviated Physical Exam			X						
Vitals Assessment ⁴		X	X		X	X	X	X	X
CBC Panel		X							
Prothrombin Test (PT)		X							
Partial Thromboplastin Time (PTT)		X							
Urinalysis		X	X ⁹	X ⁵	X ⁵	X ⁵	X ⁵	X ⁵	X ⁵
Transrectal US	X		X						X
MRI protocols	X ²			X ⁶		X			X
Biopsy ^{7,8}	X ²								X
PSA	X ²				X	X	X	X	X
UCLA-EPIC Urinary Questionnaire		X			X	X	X	X	X
IPSS & IPSS-QoL Questionnaire		X			X	X	X	X	X
IIEF-15 Potency Questionnaire		X			X	X	X	X	X
EQ-5D Questionnaire		X			X	X	X	X	X
NanoKnife System Procedure			X						
Concomitant Medications		X	X	X	X	X	X	X	X
Adverse Event Assessment			X	X	X	X	X	X	X

1. Must be signed and dated prior to completing any study procedures.
2. Must be completed within 180 days prior to enrollment in the study. PSA for enrollment must be completed prior to biopsy, or must be taken more than 30 days after biopsy.
3. Complete within 30 days prior to NanoKnife System treatment.
4. Vitals assessments include height and weight, temperature, BP, respiration rate and pulse. Note, height only needs to be collected at Baseline.
5. Complete only if there is a question of an active UTI.
6. Complete only if clinically indicated (i.e., the subject is experiencing unexpected adverse events following treatment).
7. Transperineal or Transrectal Prostate Biopsy (template mapping and/or limited targeted).
8. Complete at additional time points if subject has a lesion ≥ PI-RADS 3 on the 3-month MRI, experiences biochemical failure as defined by the Phoenix criteria as nadir + 2 ng/mL, or upon clinical suspicion.
9. Complete pre-treatment, and at discharge only if there is a question of an active UTI.
10. Complete within 3 to 10 days of NanoKnife System treatment. This visit can be conducted over the phone, as long as urinalysis and MRI are not clinically indicated.

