IPSS and IPSS-QoL³: The total score from the IPSS (International Prostate Symptom Score) and IPSS-QoL questionnaire will be presented for each visit (i.e., 1, 3, 6, 9, and 12 month follow-up). In addition, the 6-month and 12-month change from baseline will also be tabulated. See **Appendix E – Subject Questionnaires – 1.2 IPSS and IPSS-QoL** section for more details on the questionnaire and scoring instructions.

IIEF-15⁴: The IIEF-15 (International Index of Erectile Function 15 items) will have the Total Satisfaction Score and each of the 4 subscales (Erectile Function, Intercourse Satisfaction, Orgasmic Function, and Sexual Desire) will be presented for each visit (i.e., 1, 3, 6, 9, and 12 month follow-up). In addition, the 6-month and 12-month change from baseline will also be tabulated. See **Appendix E – Subject Questionnaires – 2.1 IIEF-15** section for more details on the questionnaire and scoring instructions.

PSA: The mean PSA levels at each visit, the overall percent reduction in PSA levels from baseline to each visit, and the proportion of subjects with a PSA reduction compared to baseline at each visit will be presented. Mean PSA nadir and post-nadir PSA values through 12 months post-treatment will be summarized.

Prostate Volume: The mean prostate volume at each visit, the overall percent reduction in prostate volume from baseline to each visit, and the proportion of subjects with reduction in prostate volume compared to baseline at each visit will be presented, as measured by mpMRI.

Evaluation of Prostate Tissue by mpMRI: The number and proportion of subjects determined to have cancer-bearing prostate tissue lesions on the 12-month mpMRI will be presented.

Secondary or Adjuvant Treatment: The number and proportion of subjects undergoing secondary or adjuvant treatment during the study will be presented.

EQ-5D⁵: The EQ-5D (EuroQoL – 5 Dimensions) will have the Total score and each of the 5 subscales (Mobility, Self-care, Usual activities, Pain/Discomfort, Anxiety/Depression) presented for each visit (i.e., 1, 3, 6, 9, and 12 month follow-up). In addition, the 6-month and 12-month change from baseline will also be tabulated. See **Appendix E – Subject Questionnaires – 3.1 EQ-5D** section for more details on the questionnaire and scoring instructions.

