12.7.5 Effectiveness of Therapy by Measurement of PSA Kinetics

The mean PSA levels at each visit, the overall percent reduction in PSA levels (ng/mL) from screening to each visit (1, 3, 6, 9, and 12 month follow-up), and the proportion of subjects with a PSA reduction compared to screening at each visit will be presented. If a subject is re-treated during the study, all PSA values collected following the re-treatment will not be included in the analyses but will be included in the listings. Mean PSA nadir and post-nadir PSA values through 12 months post-treatment will be summarized. Kaplan-Meier analysis and summary statistics for time, including median time to event and associated 95% CI will be presented for PSA nadir. For this assessment, our baseline will be the screening measurements.

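### Protocol and SAP disagree on the pre-treatment PSA: 4.6.13 draws it at Baseline, but SAP 12.7.5 measures reduction from a screening value that, at worst, can be 210 days old or older at treatment

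*Combined protocol and SAP*

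**What the plan says.** **Texts that point to a Baseline PSA**

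- Protocol 4.6.13 (Laboratory Tests), on serum PSA: "Blood samples will also be collected at the Baseline visit and the 1, 3, 6, 9, and 12 month follow-up visits". It then names the blood count as a further Baseline test, so the Baseline draw is for PSA.
- Protocol 6.9, PSA paragraph, reports "the overall percent reduction in PSA levels from baseline to each visit".

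**Texts that have none**

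- Protocol 4.4.2 lists the Baseline blood tests as blood count, PT and PTT only.
- Protocol 4.6.16, in the paragraph beginning "Blood samples, as obtained from the above laboratory test procedure, will be used to determine", places the pre-treatment PSA at the screening visit.
- Protocol Table 4-4 and SAP Table 1 mark PSA at Screening and at Months 1, 3, 6, 9 and 12. The Baseline column is empty.

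**The analysis rule**

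- SAP 12.7.5 computes percent reduction, and the proportion of subjects with a reduction, from screening: "For this assessment, our baseline will be the screening measurements".
- SAP 10.1 describes Baseline as the visit between Screening and treatment, with its assessments within 30 days of treatment.
- SAP 6.1 (Changes from Protocol) does not mention the PSA reference.

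**The timing rules**

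- Table 4-4 footnote 2, attached to the screening PSA: "Must be completed within 180 days prior to enrollment in the study".
- Protocol 4.2: "Subjects will be considered enrolled in the study after consent has been obtained".
- Table 4-4 footnote 3, attached to Baseline: "Complete within 30 days prior to NanoKnife System treatment".
- Protocol 4.4 allows Screening and Baseline to be combined. No maximum interval is given when they are separate.

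**The concern.** The trial has one arm, so each man's pre-treatment PSA is the only comparator for two reported results: percent reduction at five follow-up visits and the proportion of men with any reduction. If that value was taken months before the procedure, whatever PSA did in between is counted as part of the treatment effect, by an amount that differs between men.

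The protocol provides in one place for a value at most 30 days old. The SAP uses a value that may be seven months old, and does not declare the choice as a departure from 6.9. Someone reading 6.9 beside the results tables would take "baseline" to mean the Baseline visit, when the figure in fact starts from screening.

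**Working it through.** The documents give no figure for the age of the PSA at treatment, so there is nothing of theirs to reproduce.

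**1. Age of the reference value at treatment**

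Maximum age = (PSA to consent) + (consent to Baseline) + (Baseline to treatment) = 180 + *k* + 30 days.

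The 180 comes from Table 4-4 footnote 2, with enrollment set at consent by 4.2. The 30 comes from footnote 3. The gap *k* is 0 when the visits are combined and has no stated maximum otherwise, so non-zero values below are assumptions.

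| *k* (days) | Maximum age under SAP 12.7.5 |
|---|---|
| 0 (combined) | 210 |
| 1 | 211 |
| 14 | 224 |
| 30 | 240 |
| 60 | 270 |
| 90 | 300 |

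With a PSA drawn at the Baseline visit as in 4.6.13, the maximum is 30 days whatever *k* is.

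**2. Effect on the reported fall**

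Assumptions, none from the documents: PSA rises at a steady yearly rate *r* before treatment, and the true fall from the at-treatment value is 60%.

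- Drift over *t* days: d = (1 + *r*)^(*t*/365) − 1.
- Reported fall = 1 − 0.40 × (1 + d), so the shift is 0.40 × d.

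| *r* per year | d at 210 days | Shift at 210 days | d at 30 days | Shift at 30 days |
|---|---|---|---|---|
| 5% | 2.8% | 1.1 points | 0.4% | 0.2 points |
| 10% | 5.6% | 2.3 points | 0.8% | 0.3 points |
| 20% | 11.1% | 4.4 points | 1.5% | 0.6 points |

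A rising PSA makes the reported fall too small. A falling PSA does the opposite. With *r* = −5%, −10% and −20%, the factor (1 + *r*)^(210/365) is 0.971, 0.941 and 0.880, and the reported falls are 61.2%, 62.4% and 64.8% instead of 60%.

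The size depends on the assumed rate. With assumed doubling times of 10 down to 2 years, a true 60% fall would be reported as 58.4% down to 51.2% at 210 days, and as 57.9% down to 48.3% at 270 days.

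**3. Effect on the proportion with a reduction**

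A man counts as reduced if his follow-up PSA is below the screening value. After an upward drift d, that requires a true fall of more than 1 − 1/(1 + d). For the three drifts at 210 days this is 2.8%, 5.3% and 10.0%. Only men with small true falls can be misclassified.

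**4. What does not use the reference value**

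SAP 10.4 defines nadir as the lowest value after the procedure. SAP 10.6.1 counts time to nadir from the treatment date. The nadir + 2 ng/mL trigger in protocol 4.6.16 uses the nadir. None of these involves the pre-treatment PSA, and neither do the biopsy and adverse-event endpoints.

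**The case against.** The strongest reply is that 4.6.13 is the slip. Four places have no Baseline PSA, and SAP 12.7.5 follows them openly and with one rule for every subject. SAP 12.7.6 uses the same convention for prostate volume, and the SAP change history records clarifications of screening versus baseline, so the choice looks deliberate. The proposed rule would mix values at most 30 days old with values of 210 days or more. The endpoint is secondary, the protocol says the study is not powered for such claims, and SAP 12.7.5 plans no test of PSA change.

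Much of this stands. The SAP rule is uniform, the consequences are limited, and the mixing of ages is a real cost that calls for a sensitivity analysis. But a majority of passages does not remove the conflict: 4.6.13 still instructs a Baseline draw, 6.9 still says baseline, and SAP 6.1 is silent.

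Four stronger readings might be inferred, and the documents do not support them.

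- *That every PSA change starts from a value more than 210 days old.* The rule applies to every such summary, but the age is a worst case. With combined visits 210 days cannot be exceeded.
- *That the choice favours the device.* The direction depends on how PSA moves before treatment, and a rising PSA works against the device.
- *That the whole PSA endpoint is compromised.* Nadir and time to nadir do not use the reference.
- *That sites following different passages would feed different values into the analysis.* Under the present SAP all subjects contribute the screening value. Whether a Baseline PSA field exists cannot be checked, because the case report form is not in the documents.

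**Conclusion.** The point holds as an inconsistency with a modest effect on the analysis. The protocol contradicts itself on whether PSA is drawn at Baseline, and the SAP settles on the screening value without declaring the departure from 6.9. The 210-day ceiling, and the absence of any ceiling with separate visits, follow from the stated windows alone.

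The shift of about 1.1 to 4.4 percentage points rests on three assumptions: an upward drift of 5 to 20% per year, a true fall of 60%, and a PSA at the 210-day extreme. Subjects with more recent values are affected less. The point should be corrected because this is the only comparator for those two results and a better one is already provided for in the protocol. It does not threaten the trial's main conclusions.

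**What to change.** 1. Reconcile the protocol to 4.6.13. Mark PSA in the Baseline column of Table 4-4 and SAP Table 1, and bring 4.4.2 and 4.6.16 into line. Use the blood draw already made for the Baseline tests, and keep the existing rule that PSA is taken before biopsy or more than 30 days after it. The screening PSA stays the eligibility value.
2. In SAP 12.7.5, define baseline PSA as the last valid value before NanoKnife treatment, where valid means meeting the biopsy rule. Use the screening value when there is no such Baseline value.
3. State the reference definition in SAP 6.1.
4. As a sensitivity analysis, repeat the percent-reduction and proportion-reduced summaries with the screening value for all subjects, because the fallback mixes ages. Tabulating the age of the reference PSA at treatment would let a reader judge the difference.

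**Cost.** Two table corrections, short text edits, one extra set of summaries, and at most one added assay per subject at sites that had followed Table 4-4. Subjects already treated without a Baseline PSA keep the screening value, so mixed ages cannot be avoided for them.

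If the sponsor prefers to keep screening as the reference, the minimum is to correct 4.6.13 and 6.9, list the choice in SAP 6.1 and report the age of the PSA at treatment. That removes the contradiction but leaves the older reference in place.

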12.7.6 Assessment of Changes in Prostate Volume Measured via mpMRI

The mean prostate volume at each visit, the overall percent reduction in prostate volume from screening to 12 month follow-up, and the proportion of subjects with reduction in prostate volume compared to screening at 12 month follow-up will be presented, as measured by mpMRI. For this assessment, our baseline will be the screening measurements.

12.7.7 Assessment of Ablation Effectiveness by Evaluation of Prostate Tissue by mpMRI

The number and proportion of subjects determined to have cancer-bearing prostate tissue lesions (i.e., modified prostate imaging reporting and data system [PI-RADS] 3 or higher lesion) on the 3 and 12-month mpMRI will be presented.

12.7.8 Assessment of Need for Secondary or Adjuvant Treatment Following Treatment with the NanoKnife System

The number and proportion of subjects undergoing secondary or adjuvant treatment during the study will be presented. Additional information regarding reason (positive unscheduled biopsy [in-field or out-of-field], clinical progression, biochemical progression, or other), location (index lesion or contralateral lesion), and type of re-retreatment (re-treatment with IRE, radical prostatectomy, high-intensity focused ultrasound [HIFU], cryotherapy, or other) will also be presented.

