4.3.1 Inclusion Criteria

A subject is required to fulfill all of the following criteria to be included in the study:

1. Is greater than 50 years of age

2. Has at least a 10-year life expectancy
3. Has histologically confirmed organ-confined prostate cancer, clinical stage \leq T2c
4. Has a PSA \leq 15 ng/mL or PSA density < 0.15 ng/mL² if PSA is > 15 ng/mL
5. Has Gleason score 3+4 or 4+3
6. Has no evidence of extraprostatic extension by mpMRI
7. Has no evidence of seminal vesicle invasion by mpMRI, and if suspected, confirmed by biopsy
8. Physician is able to visualize prostate gland adequately on transrectal ultrasound imaging during qualifying biopsy
9. Has a transperineal or transrectal targeted prostate biopsy of lesion, plus 10-14 core systematic biopsy to include adequate sampling of the peripheral zone correlating with an intermediate risk lesion³ in the area of the MR-visible lesion
10. A visible lesion on mpMRI that is accessible to Irreversible Electroporation (IRE) treatment (Note: prostate cancer detected via systematic standard biopsy outside of the adjacent sextant location of the MRI visible lesion will meet entry criterion provided the positive core is Gleason 6; has fewer than 3 prostate biopsy fragments/cores positive and $\leq 50\%$ cancer in each of those fragments/cores on standard biopsy)
11. Is willing and able to sign a written informed consent and in the judgment of the physician, the study is in the best interest of the subject
12. Understands and accepts the obligation and is logistically able to present for all scheduled follow-up visits

4.3.2 *Exclusion Criteria*

A subject will be excluded from the study if they meet any of the following criteria:

1. Has known hypersensitivity to pancuronium bromide, atracurium or cisatracurium
2. Is unfit for anesthesia or has a contraindication for agents listed for paralysis
3. Has an active urinary tract infection (UTI)
4. Has a history of bladder neck contracture
5. Is interested in future fertility
6. Has a history (within 3 years) of inflammatory bowel disease
7. Has a concurrent major debilitating illness
8. Had active treatment for a malignancy within 3 years, including malignant melanoma, except for prostate cancer or other types of skin cancer
9. Has any active implanted electronic device (e.g., pacemaker)
10. Is unable or unwilling to catheterize
11. Has had any prior or current prostate cancer therapy, including:
 - a) Biologic therapy for prostate cancer

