4.6 Study Procedure

Subjects will be placed in the dorsal lithotomy position under sterile technique. The NanoKnife System procedure will be carried out under general anesthesia. A Foley catheter will be placed to aid in draining the bladder during treatment.

Prior to treatment with the NanoKnife System, subjects will receive Ciprofloxacin 400 mg or another antibiotic of choice selected by the treating physician per institutional guidelines via intravenous infusion to reduce the chance of infection. Subjects will be dosed according to the Dosage Guidelines in the product package insert of the chosen antibiotic. Institutional guidelines should also be followed regarding pre-operative heparin.

The area of the prostate that was positive for cancer-bearing tissue based on the mpMRI and transperineal or transrectal prostate biopsy will be targeted for focal ablation via the NanoKnife System. Only the prostate cancer-bearing tissue will be targeted for ablation, however, a treatment margin of greater than or equal to 5 mm around the Gleason 3+4 or 4+3 (intermediate-risk) lesion should be included. Note: if on biopsy, the subject was found to have a lesion in the contralateral hemisphere of the prostate that is Gleason 6 and comprises no more than 6 mm linear extent of prostate-bearing tissue in a single core, this lesion should not be treated.

An MRI/transrectal ultrasound (TRUS) fusion device or standard TRUS probe may be placed in the rectum to visualize the prostate in both sagittal and axial views. The ultrasound grid which was used during the mapping biopsy will be oriented using anatomical landmarks and used to identify the location of the positive biopsy cores. The NanoKnife Single Electrode Probes will be surgically inserted into the prostate through the perineum using MRI/TRUS fusion guidance and the ultrasound grid for guidance. The location of the probes will be documented via ultrasound imaging and notation in the Case Report Form (CRF).

Further details of the further details of the procedures listed below can be found in the Clinical Study Guide provided.

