6.7 Primary Effectiveness Endpoint

The primary efficacy endpoint is the rate of subjects with a negative in-field biopsy at 12 months. The number and proportion of subjects obtaining a negative in-field biopsy at 12 months will be presented, along with the 95% confidence interval of the proportion.

Subjects who are biopsied prior to 12 months (if there are positive findings on the 3-month mpMRI, if the subject is deemed to have biochemical progression, or if the treating physician deems there to be clinical suspicion) and have a positive in-field biopsy will be imputed as failures for the analysis of the primary efficacy endpoint. Note: Subjects with early positive out-of-field biopsies will not be considered failures for the primary efficacy endpoint.

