9.2 Secondary Endpoint

The secondary outcomes that will be evaluated are:

- Rate of negative in-field biopsy at 12 months as defined by the Delphi consensus criterion of absence of clinically significant disease (≤ 3 mm of Gleason ≤ 6 disease in any biopsy core is insignificant) ([Postema et al., 2016](#)).
- Assessment of urinary function by comparison of pre- and post-operative UCLA-EPIC Urinary Domain ([Wei et al., 2000](#)), IPSS ([Barry et al., 1992](#)), and IPSS-QoL scores ([Rees, 2013](#)).
- Assessment of erectile function by comparison of pre- and post-operative IIEF-15 potency scores ([Rosen et al., 2002](#)).
- Effectiveness of therapy by measurement of PSA kinetics including time to PSA nadir.
- Assessment of changes in prostate volume by comparison of pre-treatment and 12-month prostate volume measured via mpMRI.
- Assessment of ablation effectiveness by evaluation of prostate tissue by mpMRI at 3 months post-treatment and at 12 months post-treatment.
- Assessment of need for secondary or adjuvant treatment following treatment with the NanoKnife System.
- Evaluation of subject reported pre- and post-operative QoL using the EQ-5D® ([Oppe et al. 2014](#)).

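### The mpMRI ablation-effectiveness proportion in SAP 12.7.7 has no location limit, so it mixes findings in the treated area with out-of-field disease

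*Combined protocol and SAP*

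**What the plan says.** SAP 9.2 lists as a secondary endpoint "Assessment of ablation effectiveness by evaluation of prostate tissue by mpMRI at 3 months post-treatment and at 12 months post-treatment". SAP 12.7.7 turns this into the "number and proportion of subjects determined to have cancer-bearing prostate tissue lesions", and defines such lesions as "i.e., modified prostate imaging reporting and data system [PI-RADS] 3 or higher lesion) on the 3 and 12-month mpMRI". The analysis paragraph in protocol 6.9 is similar but narrower. It covers one time point and gives no PI-RADS cut-off: "The number and proportion of subjects determined to have cancer-bearing prostate tissue lesions on the 12-month mpMRI will be presented". No in-field or ablation-zone condition is attached to this endpoint in SAP 9.2, SAP 12.7.7, protocol 3.5.2 or protocol 6.9.

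Other parts of the plan do depend on location:

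- Protocol 4.6 confines ablation to the targeted cancer-bearing tissue plus a margin. Of a small contralateral Gleason 6 lesion found on biopsy it says "this lesion should not be treated".
- Inclusion criterion 10 (protocol 4.3.1) states that "prostate cancer detected via systematic standard biopsy outside of the adjacent sextant location of the MRI visible lesion will meet entry criterion", subject to limits on grade, number of cores and extent.
- Protocol 4.6.16 makes the 12-month biopsy in-field and provides for biopsy of untreated tissue when the 12-month MRI shows a new suspicious lesion there.
- Protocol 6.7 states: "Subjects with early positive out-of-field biopsies will not be considered failures for the primary efficacy endpoint". SAP 12.7.1 repeats this in a footnote.
- SAP 12.7.8, the next section, splits re-treatment by in-field or out-of-field biopsy and by index or contralateral lesion.

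**The concern.** The endpoint's name asks whether the treated tissue was ablated. The counting rule asks whether the subject has a suspicious lesion on MRI. With focal treatment these are different questions. A man whose target is fully ablated, but who has a PI-RADS 3 or higher lesion in tissue that nobody treated, is counted with men who have a residual lesion in the ablation zone.

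Two things are lost. The proportion cannot be read as an imaging measure of ablation, and it cannot sensibly be compared with the primary endpoint, which is strictly in-field. The rate of out-of-field lesions on MRI, which matters in its own right after focal therapy, also cannot be recovered from the one figure.

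**Working it through.** **Does any text limit the count by location?** I compared the four places where the endpoint is defined or analysed.

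| Place | Measure | Time points | Location limit |
|---|---|---|---|
| Protocol 3.5.2 | evaluation of tissue by mpMRI | 3 and 12 months | none |
| Protocol 6.9 | subjects with cancer-bearing lesions | 12 months in the analysis paragraph | none |
| SAP 9.2 | evaluation of tissue by mpMRI | 3 and 12 months | none |
| SAP 12.7.7 | subjects with a PI-RADS 3+ lesion | 3 and 12 months | none |

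An analyst following SAP 12.7.7 literally would count a qualifying lesion in any sector.

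**Can out-of-field lesions reach the count?** Yes, by two routes. Tissue outside the target is left untreated and may already contain Gleason 6 disease (protocol 4.3.1 and 4.6). New lesions may also appear there (protocol 4.6.16). In either case the lesion counts only if it is read as PI-RADS 3 or higher.

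**How large could the mixing be?** The plan states no rate for this endpoint, so there is no figure to reproduce. For illustration, let q be the proportion of subjects with an in-field PI-RADS 3+ lesion and r the proportion with one outside the field. Both are assumed. If the two are independent:

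- reported proportion = 1 − (1 − q)(1 − r)
- excess over the in-field proportion = (1 − q) × r

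| q | r | Reported | Excess (points) | Counted only for out-of-field lesions, of 118 | Share of all counted |
|---|---|---|---|---|---|
| 10% | 5% | 14.5% | 4.5 | 5.3 | 31% |
| 10% | 10% | 19.0% | 9.0 | 10.6 | 47% |
| 10% | 20% | 28.0% | 18.0 | 21.2 | 64% |
| 20% | 5% | 24.0% | 4.0 | 4.7 | 17% |
| 20% | 10% | 28.0% | 8.0 | 9.4 | 29% |
| 20% | 20% | 36.0% | 16.0 | 18.9 | 44% |
| 30% | 5% | 33.5% | 3.5 | 4.1 | 10% |
| 30% | 10% | 37.0% | 7.0 | 8.3 | 19% |
| 30% | 20% | 44.0% | 14.0 | 16.5 | 32% |

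The 118 is the planned number of subjects and assumes that all are imaged.

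**Without independence.** The excess is r minus the proportion with both kinds of lesion, so it lies between r − min(q, r) and r. At q = 30%, r = 5% that is 0 to 5 points. At q = 10%, r = 20% it is 10 to 20 points. The excess is never negative and disappears only if every man with an out-of-field lesion also has an in-field one.

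**The case against.** A reader might infer that the SAP scores out-of-field lesions as ablation failures. It does not. SAP 12.7.7 neither uses the word failure nor says that the whole gland is counted. The whole-gland reading follows only from the absence of a limit.

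A reader might also infer that the trial's conclusion is biased against the device. That is not supported either. The formal test of ablation effectiveness is the in-field biopsy rate, which already sets early out-of-field positives aside. The mpMRI proportion has no hypothesis, threshold or comparator, and protocol 6.2 says the study is not powered for claims on secondary endpoints.

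There is also a case for a gland-wide count. Protocol 4.6.16 gives the 3-month mpMRI two purposes, checking that the planned area was covered and assessing progression. The PI-RADS 3 cut-off is the same as the early-biopsy trigger, which has no location limit. On this view the count is a coherent measure of suspicious MRI and only its title is too narrow. That supports keeping the count. It does not make the count a measure of ablation.

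The route through untreated Gleason 6 disease is narrower than it may seem. Those foci are described as detected on biopsy, and nothing says they are visible on MRI. Nor is out-of-field disease wholly hidden, since SAP 12.7.8 tabulates it. But that table covers only subjects who had secondary or adjuvant treatment.

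Finally, the study has no blinding mechanism (SAP 6.0), and an in-field count can only be equal to or lower than the stated one. Replacing the stated count would therefore be less safe than adding to it. That point stands and shapes the fix.

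**Conclusion.** The point holds as a mismatch between an endpoint's name and its counting rule. As written, SAP 12.7.7 gives one proportion that mixes in-field residual findings with out-of-field disease, although the primary endpoint and SAP 12.7.8 both keep them apart. That proportion does not isolate the ablation effect.

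The direction is known: the mixed count is at least as high as the in-field count. The size is not known, because the documents give no lesion rates. The excess of about 3.5 to 18 points rests wholly on assumed rates (in-field 10% to 30%, out-of-field 5% to 20%) and on independence. It shows what is possible and is not an estimate. The primary endpoint and its test are untouched. This is a cheap improvement to a descriptive table.

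**What to change.** In SAP 12.7.7, keep the stated all-lesion count and add these rows at both 3 and 12 months:

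- (a) subjects with a PI-RADS 3 or higher lesion in or touching the treated area, named as the ablation-effectiveness measure;
- (b) subjects with a PI-RADS 3 or higher lesion outside it, split into present before treatment and new.

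State that one subject can appear in more than one row, so the rows need not add up to the all-lesion count. Record the addition in SAP 6.1 before database lock.

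No extra imaging is needed. Protocol 4.6.15 already uses mpMRI to document lesion location, and the 12-month decision on biopsying untreated tissue already requires a judgement on whether a lesion is new and outside the treated area.

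There are two costs. Border lesions need a stated allocation, and counting them as in-field is the cautious choice. The CRF content is not available here, so if it holds no in-field flag for MRI lesions, location will have to be taken from the MRI report.
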